# 1 Introduction

Objectives	
1 Primary Objective
 
To compare the effects of knee OA educational information, with and without pathoanatomical content, on i) beliefs about the necessity to have an x-ray to confirm an OA diagnosis, and ii) beliefs about the necessity of joint replacement surgery in adults who have not had a knee joint replacement.
 
2 Secondary Objectives
 
To compare the effects of knee OA educational information, with and without pathoanatomical content, on management beliefs (about exercise and physical activity, the safety of exercise, medications, x-rays to determine treatment), level of concern, and OA knowledge in adults who have not had a knee joint replacement.
 
To explore whether a history of knee pain in the last 3 months moderates the effect of knee OA educational information without pathoanatomical content on the two primary outcomes, i) beliefs about the necessity to have an x-ray to confirm an OA diagnosis, and ii) beliefs about the necessity of joint replacement surgery in adults who have not had a knee joint replacement.

Study Design	Two-arm, parallel groups superiority randomised controlled trial.
Planned Sample Size	556 participants.
Study Procedures	
The entire trial will be administered in one single online survey. Participants will initially complete screening questions within the survey to determine eligibility. Eligible participants will then complete baseline outcome measures before being randomly allocated to one of two groups, both of whom will then be asked to immediately read a digital information pamphlet about knee OA on screen:
 
i) Control group: the pamphlet will contain information about OA including biological pathoanatomical information and language about OA
 
ii) Experimental group: the same pamphlet as the Control group, but with all pathoanatomical information and language relating to the structure of an OA joint removed.

	
All participants will complete outcome measures again, immediately after reading their allocated digital information pamphlet.

Duration of the study
	
Anticipated participant recruitment start: June 2022  Anticipated data collection end: June 2022
 
Based on our previous similar study [1], which recruited 735 participants in four days through a similar mechanism, we anticipate recruitment for this RCT will take approximately 6 days.

Figure 1. Study chart

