## 3 Analysis Objectives

The aim of this study is to compare the effects of knee OA educational information, with and without pathoanatomical content, on consumer OA management beliefs in adults who have not had a knee joint replacement.

### 3.1 Aim 1

To compare the effects of knee OA educational information, with and without pathoanatomical content, on i) beliefs about the necessity to have an x-ray to confirm an OA diagnosis, and ii) beliefs about the necessity of joint replacement surgery in adults who have not had a knee joint replacement.

We hypothesise that removing pathoanatomical content will lead to lower beliefs that an x-ray is necessary to confirm an OA diagnosis and lower beliefs that joint replacement surgery is necessary, compared to information with pathoanatomical content.

### 3.2 Aim 2

To compare the effects of knee OA educational information, with and without pathoanatomical content, on management beliefs (about exercise and physical activity, the safety of exercise, medications, x-rays to determine treatment), level of concern, and OA knowledge in adults who have not had a knee joint replacement.

We secondarily hypothesise that removing pathoanatomical content will lead to higher beliefs that exercise and physical activity is necessary and is safe, lower beliefs that medication is necessary, lower beliefs that x-rays are required to determine treatment, lower levels of concern, and higher OA knowledge.

To explore whether a history of knee pain in the last 3 months moderates the effect of knee OA educational information without pathoanatomical content on the two primary outcomes, i) beliefs about the necessity to have an x-ray to confirm an OA diagnosis, and ii) beliefs about the necessity of joint replacement surgery in adults who have not had a knee joint replacement.

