## 4 Analysis sets/Populations/Subgroups

Inclusion Criteria

Participants will be eligible for the study if they meet the following inclusion criteria:

- i) Aged 45 years or over;
- ii) Have (n=278), or have not (n=278), experienced any activity-related knee joint pain in the past 3 months;
- iii) Currently living in Australia.

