## 7 Statistical Methodology

### 7.1 Statistical Procedures

A biostatistician ([name], supervised by [name]) will analyse de-identified data in Stata version 16.1 (StataCorp LLC, College Station, TX, USA), while blind to group name. Descriptive data will be presented by intervention group as mean (SD), median (IQR) or n (%) as appropriate. Comparative analyses between groups will be performed using intention-to-treat according to the group to which the participant was randomised, irrespective of whether they adhered to the intervention by reading the information. The number included in each analysis will be reported. Standard diagnostic plots will be used to check model assumptions, including assessing linearity and homoscedasticity, where appropriate.

#### 7.1.1 Aim 1

Separate linear regression models for each primary outcome will be used to estimate the between-group mean (95% confidence interval, CI) difference in post-intervention scores, adjusted for the outcome at baseline. Post-intervention time point was 'immediately following reading a digital information pamphlet about knee OA on screen'.

#### 7.1.2 Aim 2

Separate linear regression models for each continuous secondary outcome will be used to estimate the between-group mean (95% CI) difference in post-intervention scores, adjusted for the outcome at baseline. For the ordinal secondary outcome, level of concern, ordinal logistic regression models will be fitted similarly, adjusted for the outcome at baseline. The proportional odds assumption will be assessed using the Brant test. If proportional odds cannot be assumed, multinomial regression models will be fitted. Results will be reported as odds ratios, or relative risk ratios if multinomial regression is used, with corresponding 95% CIs.

The mean (95% CI) effect on each of the primary outcomes, i) beliefs about x-rays and ii) beliefs about joint replacement surgery, of potential moderators, i) a history of knee pain in the past 3 months, ii) highest education level (as a binary variable, no tertiary versus some tertiary) and iii) ever sought care for knee pain from any healthcare provider for each group will be estimated using separate linear regression models for each outcome and each moderator, with an interaction term fitted between group and the potential moderator, adjusting for baseline scores of the relevant primary outcome.

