## 7.2 Measures to Adjust for Multiplicity, Confounders, Heterogeneity

We have two primary outcomes and so have adjusted the alpha for each primary outcome to 0.025 to give an overall alpha of 0.05 across both outcomes. We have several secondary outcomes. All secondary outcomes are exploratory and not powered for. We will therefore not adjust for multiple secondary outcomes but instead report all effect sizes, confidence intervals, and p values in order to let readers use their own judgment about the relative weight of the conclusions. This approach aligns with the usage of p-values favoured by the American Statistical Association [3].

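### The linear outcome models could add knee pain, the factor on which recruitment is fixed at 278/278; the planned model is valid, so this is a small, nearly costless improvement

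*SAP*

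**What the plan says.** Section 7.1.1 fits a separate linear regression for each primary outcome and reports the between-group "difference in post-intervention scores, adjusted for the outcome at baseline". Section 7.1.2 uses the same form for the continuous secondary outcomes. No other covariate enters these models.

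Knee pain has a prominent place elsewhere in the SAP:

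- Section 4 builds the sample in two equal halves on it: "Have (n=278), or have not (n=278), experienced any activity-related knee joint pain in the past 3 months". Together these make the "556 participants" of section 1.
- Section 3.2 makes it the only moderator named in the objectives: "To explore whether a history of knee pain in the last 3 months moderates the effect of knee OA educational information without pathoanatomical content". The methods in 7.1.2 add education and care-seeking as further moderators.
- Section 6 puts it in the imputation model, which is used only if more than 5% of either primary outcome is missing.

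On timing, section 1 places the eligibility screen first, and then: "Eligible participants will then complete baseline outcome measures before being randomly allocated to one of two groups". Knee-pain status is therefore a pre-randomisation variable, and the quota requires it to be known for every participant. The SAP names no stratification factor for the allocation.

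**The concern.** Beliefs about x-rays and joint replacement may differ between people with and without recent knee pain, even among those with the same baseline score. If so, leaving knee pain out keeps that variation in the error term, and a chance difference between arms in the share with knee pain passes into the estimate. The SAP gives no reason for omitting the one variable that structures its sample.

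At stake are a little precision and, in the trial actually run, a possible small shift in the headline estimates. The validity of the primary test is not at stake.

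**Working it through.** **Inputs from the SAP.** Total 556; quotas 278 and 278; "Two-arm, parallel groups superiority randomised controlled trial"; and alpha, where the plan has "adjusted the alpha for each primary outcome to 0.025 to give an overall alpha of 0.05 across both outcomes".

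**Assumptions.** The SAP does not give these: 1:1 allocation (278 per arm), two-sided tests, the share of residual variance that knee pain explains after the baseline score (partial R², taken as 0% to 5%), and the knee-pain difference in post-intervention score at a given baseline score (b, taken as 0.25 to 1 point).

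**The plan's own figures.** 278 + 278 = 556 and 0.025 + 0.025 = 0.05; both agree. The power basis of 556 cannot be reproduced, because the SAP gives no effect size, SD or power.

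**Precision.** The planned model has 3 coefficients (553 residual degrees of freedom); adding knee pain makes 4 (552).

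SE ratio = √[(1 − R²) × 553/552]

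Equivalent extra participants = 556 × R²/(1 − R²)

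| Partial R² | SE ratio | Change in SE | Extra participants | Power, from nominal 80% |
|---|---|---|---|---|
| 0% | 1.001 | +0.1% | 0 | 79.9% |
| 1% | 0.996 | −0.4% | 5.6 | 80.4% |
| 2% | 0.991 | −0.9% | 11.3 | 80.8% |
| 5% | 0.976 | −2.4% | 29.3 | 82.1% |

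**Chance imbalance, if allocation was not stratified.** With 278 of 556 having knee pain and 278 per arm, the number with knee pain in one arm is hypergeometric:

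- Variance = 278 × 0.5 × 0.5 × 278/555 = 34.8, so SD = 5.90.
- SD of the difference in proportions = 2 × 5.90/278 = 0.0424.
- 95% limit = 1.96 × 0.0424 = 0.083, or 8.3 percentage points.

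Shift in the estimate at that limit = b × 0.083:

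- b = 0.25: 0.02 points
- b = 0.5: 0.04 points
- b = 1: 0.08 points

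**Validity.** Simulation with 4,000 trials per scenario, residual SD 2.2 (assumed), no treatment effect and nominal alpha 0.025:

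| Allocation | b | Mean SE, planned | Mean SE, with knee pain | Type I error, planned | Type I error, with knee pain |
|---|---|---|---|---|---|
| Unstratified | 0.5 | 0.188 | 0.187 | 0.027 | 0.028 |
| Unstratified | 1.0 | 0.191 | 0.187 | 0.023 | 0.021 |
| Stratified | 0.5 | 0.188 | 0.187 | 0.022 | 0.023 |
| Stratified | 1.0 | 0.191 | 0.187 | 0.023 | 0.028 |

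The Monte Carlo standard error of each rejection rate is √(0.025 × 0.975/4000) = 0.0025, so all rates are compatible with 0.025. Mean bias was at most 0.005 points in absolute value in every scenario.

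**The two gains are one gain seen twice.** With residual SD 2.2, the SE with knee pain in the model is 2.2 × √(2/278) = 0.187. Adding the spread of the imbalance shift at b = 1 gives √(0.1866² + 0.0424²) = 0.191, which is the planned model's SE. The precision figure is the average over allocations; the shift is what one particular allocation could bring. They should not be added together.

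**The case against.** The strongest reply is that nothing here is wrong. Regression on group and baseline score is pre-specified, unbiased and correctly sized, and its confidence interval already allows for chance imbalance. The baseline covariate is the same question asked minutes earlier, so it absorbs any knee-pain difference in prior belief and may leave little to gain. Table 1 will show any imbalance, and Table 3 reports effects by knee-pain status. All of this stands, and it limits the point to a minor one. It does not remove the point: the interval covers imbalance on average over randomisations, whereas adjustment removes it in the trial at hand, and neither table corrects the headline estimate.

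A reader might infer three stronger claims, none of which the SAP supports:

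- *That knee pain is a stratification factor, so the model must include it.* A recruitment quota fixes how many people of each kind enter; it does not balance them between arms. The SAP does not mention stratified allocation.
- *That knee pain must be prognostic because the plan calls it a moderator.* Moderation concerns a difference in treatment effect. It says nothing about variance explained beyond the baseline score. Education and care-seeking are also listed as moderators in 7.1.2, so the moderator role alone does not select knee pain.
- *That precision is certainly being lost.* The gain rests on a partial R² that the SAP does not give, and it may be nil.

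**Conclusion.** The point holds as a minor improvement. The linear models omit a pre-randomisation variable that fixes the make-up of the sample, and including it would cost almost nothing. Over the assumed range of 0% to 5% of residual variance, the SE changes by +0.1% to −2.4%, equivalent to 0 to about 29 participants. Without stratified allocation, adjustment also removes a shift of about 0.02 to 0.08 points at the 95% limit of imbalance, for an assumed association of 0.25 to 1 point. The upper value is roughly 0.4 of the simulated SE (0.08/0.19). With stratified allocation there is no such imbalance to correct, and the planned SE is, if anything, slightly too large (at b = 1, mean SE 0.191 against an empirical SD of 0.188), so the planned test errs on the cautious side.

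The figures depend on 1:1 allocation and on the assumed partial R², b and residual SD. The conclusion that the planned analysis is valid does not depend on how strongly knee pain predicts the outcome.

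**What to change.** Before outcome data are seen, amend 7.1.1 and the part of 7.1.2 on continuous secondary outcomes, so that each linear model contains group, baseline score and knee pain in the past 3 months (yes/no). Keep the baseline-only model as a supportive analysis, and update Table 2 footnote b. The choice must not wait for Table 1, because adding the covariate after seeing an imbalance would be data-driven. If allocation was in fact stratified by knee pain, say so in the SAP and give that as the reason for the term.

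Leave the ordinal and multinomial models for level of concern as planned, or state that adding knee pain changes the conditional odds ratio being estimated. The linear-model precision argument does not carry over to them unchanged.

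The cost is a few words of SAP text and one degree of freedom. The variable is already collected and already in the imputation model, so section 6 needs no change.

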### DEFINITIONS OF DERIVED VARIABLES IN THE DATA SET

Variable in data set	Unit	Variable label in spreadsheet	Calculation	Range	Better
Belief about x-ray to diagnose knee OA	11-point NRS	Xray_diag	n/a	0-10	↓
Belief about joint replacement surgery	11-point NRS	Surgery	n/a	0-10	↓
Belief about exercise and physical activity	11-point NRS	Exercise	n/a	0-10	↑
Belief about safety of exercise	11-point NRS	Exercise_damage	n/a	0-10	↓
Belief about medication	11-point NRS	Medication	n/a	0-10	↓
Belief about x-ray to determine treatment	11-point NRS	Xray_determine	n/a	0-10	↓

Knee OA knowledge scale	11 item, each scored 1-5 ordinal scale	Knowledge Know_1 Know_2 Know_3 Know_4 Know_5 Know_6 Know_7 Know_8 Know_9 Know_10 Know_11	1=false 2=possibly false 3=unsure 4=possibly true 5=true  Items 1,2, 3, 4, 7, and 11 are reverse scored and added to items 5, 6, 8, 9, and 10.	11-55	↑
Level of concern	Single item, 0-4 (ordinal)	Concern	n/a	0-4	↓

## Appendix 3

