IQR: interquartile range (25th to 75th percentile); NRS: numerical rating scale ranging from 0 ('no pain' or 'no interference') to 10 ('worst pain possible' or 'maximal interference with function').

#Rated using a 5-point scale with terminal descriptors of 1='always difficult' to 5='always easy'.

Table 2. Summary measures and estimated between-group mean differences [95% CI] or odds ratios/relative risk ratios [95% CI] for each outcome as appropriate.

Outcome	Baseline, mean (SD)		Post-intervention ^ , mean (SD)		Within-group change a , mean (SD)		Between-group difference in post-intervention scores (n=xxx)	
	Group 1 (n=xxx)	Group 2 (n=xxx)	Group 1 (n=xxx)	Group 2 (n=xxx)	Group 1 (n=xxx)	Group 2 (n=xxx)	Mean b [95% CI]	P-value
Primary outcomes*								
Belief x-ray is necessary for diagnosis c								
Belief joint replacement surgery is necessary at some stage c								
Secondary outcomes								
Belief exercise and physical activity is helpful d,¥								
Belief exercise would damage knee c,β								
Belief medication is helpful c,¥								
Belief x-ray is necessary to determine treatment c,*								
Osteoarthritis Knowledge d,§								
	Baseline, n (%)		Post-intervention, n (%)		Between-group (n=xxx)			

	Group 1 (n=xxx)	Group 2 (n=xxx)	Group 1 (n=xxx)	Group 2 (n=xxx)	Odds ratio f [95% CI]	P-value	Relative risk ratio g [95% CI]	P- value
Level of concern h					OR [95% CI]	P	–	–
1 = Not at all concerned					–	–	REFERENCE	–
2 = A little concerned					–	–	RRR [95% CI]	P
3 = Quite concerned					–	–	RRR [95% CI]	P
4 = Very concerned					–	–	RRR [95% CI]	P

SD = standard deviation.

^ Correlation of post-intervention with baseline continuous outcome scores:

- Experimental group.
- Control group.

a Within-group change was calculated as post-intervention minus baseline for all outcomes.

b Mean (95% CI) difference in post-intervention scores between groups, adjusted for the outcome at baseline, estimated using separate regression models for each outcome.

c Negative values favour Group 2.

d Positive values favour Group 2.

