f Ordinal logistic regression model fitted, adjusted for the outcome at baseline where able, as proportional odds could be assumed. Odds ratio > 1 indicate increased odds of Group 2 compared to Group 1. g Multinomial regression model fitted, adjusted for the outcome at baseline where able, as proportional odds could not be assumed. Relative risk ratios > 1 indicate increased risk of Group 2 compared to Group 1.

\*Measured using the 11-point numerical rating scale ranging from 0='definitely unnecessary' to 10='definitely necessary'.

‡ Measured using the 11-point numerical rating scale ranging from 0='definitely not helpful' to 10='definitely helpful'.

β Measured using the 11-point numerical rating scale ranging from 0='definitely would not damage it' to 10='definitely would damage it'.

§ Measured using the Knee Osteoarthritis Knowledge Scale [4]. Scores range from 11 to 55, with higher scores indicating greater knowledge about osteoarthritis.

h Question asked "if you were told by your doctor that you have knee osteoarthritis, how concerned would you be that your knee problem would get worst in the future?"

**Table 3: Moderation of the effect of the removal of pathoanatomical content in knee osteoarthritis educational information on primary outcomes using complete case data.**

Outcome	Potential moderators at baseline	Group 1 Mean (SD) [n=xxx]	Group 2 Mean (SD) [n=xxx]	Group 2 – Group 1 Mean (95% CI) [n=xxx]	Interaction p-value
Belief x-ray is necessary for diagnosis *	Knee pain in the last 3 months				
	No				
	Yes				
	Highest education level#				
	No tertiary				
	Some tertiary				
	Ever sought care for knee pain from any healthcare provider				
	No Yes				
Belief joint replacement surgery is necessary at some stage *	Knee pain in the last 3 months				
	No				
	Yes				
	Highest education level#				
	No tertiary				
	Some tertiary				
	Ever sought care for knee pain from any healthcare provider				
	No Yes				

SD=standard deviation; CI=confidence intervals.

\*Measured using the 11-point numerical rating scale ranging from 0='definitely unnecessary' to 10='definitely necessary'.

#Highest education level as a binary variable, no tertiary (primary school, secondary school, trade or trade certificate and don't know/unsure) versus some tertiary (university or tertiary institute and higher university degree).

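### Level of concern: an incompletely specified Brant rule can replace one ordered odds ratio with three unordered contrasts and no joint test, leaving no single answer to the directional hypothesis

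*SAP*

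**What the plan says.** Section 3.2 of the SAP states one directional hypothesis for this outcome, that removing pathoanatomical content lowers concern. Appendix 2 marks lower as better. The item has four ordered responses.

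Section 7.1.2 sets the analysis in four steps:

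- Model: "For the ordinal secondary outcome, level of concern, ordinal logistic regression models will be fitted similarly, adjusted for the outcome at baseline".
- Check: "The proportional odds assumption will be assessed using the Brant test". No significance level is given, nor which Brant statistic counts.
- Fallback: "If proportional odds cannot be assumed, multinomial regression models will be fitted".
- Reporting: "Results will be reported as odds ratios, or relative risk ratios if multinomial regression is used, with corresponding 95% CIs".

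In Appendix 3, Table 2 marks the row "1 = Not at all concerned" as the reference and gives each of the other three categories its own relative risk ratio and P-value. There is no cell for a joint test of group. Footnote g describes the fallback model as "adjusted for the outcome at baseline where able, as proportional odds could not be assumed". Footnote f puts the same *where able* condition on the ordinal model.

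Section 7.2 calls all secondary outcomes exploratory and unpowered.

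**The concern.** The starting analysis suits the question: one ordered comparison, one odds ratio, adjusted for baseline. The fallback does not. It ignores the order of the categories and replaces one estimate with three contrasts against one end of the scale. With no joint test, a reader cannot say from the model results whether concern was lower overall.

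The trigger is also open. The model contains group and baseline concern. An overall Brant test covers both, so it can reject because the baseline term is non-proportional while the group effect is proportional. The reported effect would then change for a reason unrelated to the pamphlet.

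Separately, section 7.1.2 adjusts for baseline without condition, while both Table 2 footnotes make adjustment conditional and give no rule for when it is dropped.

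**Working it through.** The SAP gives no power, effect size or category distribution for level of concern, so there is no figure of its own to reproduce. The check is by simulation.

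**Inputs from the SAP:** 556 participants (section 1); four ordered categories (section 5); adjustment for baseline (section 7.1.2).

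**Assumed:** 1:1 allocation, so 556 / 2 = 278 per arm (the two 278s in section 4 are knee-pain strata, not arms); two-sided 0.05, matching the 95% CIs; baseline shares of 8/32/35/25% across the categories, or 3/27/40/30% for a sparse reference; baseline entered as a score; the true odds ratios below. An odds ratio under 1 means lower concern in the experimental group.

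**Degrees of freedom.** Four categories give three cut-points. The proportional-odds group effect uses 1 df and the multinomial group effect 4 − 1 = 3. The Brant test for one term compares three slopes, so it has 3 − 1 = 2 df. With group and a baseline score, the overall test has 2 × 2 = 4 df.

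**Power, 600 trials per row.** The Monte Carlo standard error is at most about √(0.5 × 0.5 / 600) = 2 points.

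| True group effect | Ordinal, 1 df | Multinomial, joint 3 df | Three single ratios (categories 2, 3, 4 v 1) |
|---|---|---|---|
| Proportional, OR 0.65 | 73% | 57% | 13%, 35%, 58% |
| Proportional, OR 0.60 | 89% | 73% | 16%, 46%, 75% |
| Proportional, OR 0.60, reference about 2% post-intervention | 88% | 77% | 2%, 10%, 29% (unstable standard errors) |
| Graded, ORs 1.0/0.75/0.45 by cut-point | 69% | 80% | 6%, 6%, 42% |
| Crossing, ORs 0.5/1.0/1.5 by cut-point | 7% | 64% | 48%, 49%, 10% |

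With a proportional effect, moving to the joint 3-df test costs 88 − 77 = 11 to 73 − 57 = 16 points. The single ratios, which are all that Table 2 shows, do worse still. With a graded effect the joint test gains 80 − 69 = 11 points, yet the single ratios stay below the ordinal test. With a crossing effect the ordinal odds ratio has almost no power.

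**Baseline adjustment.** Without it, power of the joint multinomial test falls from 57% to 34% (OR 0.65), 73% to 49% (OR 0.60) and 77% to 53% (sparse reference), a loss of about 22 to 24 points. An unadjusted ordinal model was not simulated.

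**How often the overall Brant test rejects at 5%.** Here the group effect is proportional at OR 0.65, with about 3% to 7% in the reference category. Only the baseline slope varies across the three cut-points:

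| Baseline slopes | Overall Brant rejects |
|---|---|
| Equal | 4% |
| 1.4/1.5/1.6 | 7% |
| 1.3/1.5/1.7 | 16% |
| 1.2/1.5/1.8 | 33% to 37% |
| 1.0/1.5/2.0 | 66% to 84% |

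In the last row the group-term statistic rejected in only 3% to 5.5% of trials, close to its nominal level. The choice of statistic can therefore decide which model is reported.

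**The case against.** The strongest reply is that the fallback is prespecified, the analyst is blind to group name, and Table 2 prints counts and percentages by category, group and time point, so the direction of any shift stays visible. The outcome is one exploratory secondary. All of this stands and keeps the point minor. It does not supply a single estimate or test for the stated hypothesis.

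A second reply is that a single odds ratio is a poor summary when proportional odds fails. That also stands: under crossing effects it had 7% power against 64% for the joint test. So the remedy needs a joint test beside the odds ratio.

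A reader might infer more than the SAP supports:

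- *The switch always loses power.* It does when the group effect is proportional or nearly so. Otherwise a joint test can do better.
- *The Brant test will usually fail.* Section 7.1.2 does not say that the overall statistic decides, and the high rejection rates come from one steep assumed baseline pattern. Milder patterns gave 4% to 37%.
- *The switch causes loss of baseline adjustment.* The condition is in footnote f as well as g, so it applies to both models.
- *The reference category is ambiguous.* Appendix 2 has "Single item, 0-4 (ordinal" while Appendix 1 and Table 2 code the four responses 1 to 4. But Appendix 2 attaches no labels to its range, and Table 2 names the reference by label. This is a clerical range error.
- *The reference category will be small.* The SAP gives no distribution, so this is an assumption.

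**Conclusion.** The point holds as a minor one. Followed as written, section 7.1.2 can end with three unordered contrasts, no joint test, and no single result for the hypothesis of lower concern. The rule for getting there does not name the deciding Brant statistic or its level.

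The size depends on the truth. With a proportional group effect of OR 0.65 and 278 per arm, power is about 73% for the ordinal test, 57% for a joint multinomial test and 13% to 58% for the single ratios reported. With non-proportional group effects a joint test can beat the single odds ratio. Every figure rests on assumed category shares, baseline effects and odds ratios. The type I error of the two-stage rule was not evaluated.

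The mismatch between section 7.1.2 and footnotes f and g is a plain inconsistency, whichever model is preferred. No conclusion on the primary outcomes is affected.

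**What to change.** In section 7.1.2:

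1. Report the baseline-adjusted proportional-odds ratio with its 95% CI whatever the Brant result.
2. Base the decision on the Brant statistic for the group term, and state its significance level.
3. If only baseline concern fails, relax that term alone and keep one group odds ratio.
4. If the group term fails, replace the multinomial fallback with a partial proportional-odds model. Report its three cumulative odds ratios and a joint 3-df group test beside the average odds ratio.

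In Table 2, replace the relative-risk-ratio columns accordingly, rewrite footnote g for the new model, and delete *where able* from footnotes f and g so that they match section 7.1.2. In Appendix 2, correct the range to 1-4.

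The cost is a few lines of SAP text and a little more analysis. The single odds ratio remains only an average and has little power under crossing effects, which the joint test is there to cover. That test was not simulated itself. I take its power to be close to that of the multinomial 3-df test, since both spend three parameters on the group effect.
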